5.3.3 Part 3 Exploratory Endpoints

- CD38 expression on MM cells and other immune cells within the bone marrow and its correlation with clinical outcome.
- Evaluation of somatic mutations and polymorphisms and their associations with response and/or acquired resistance.
- Evaluation of anti-interferon antibodies at baseline and correlation with response.
- Rate of MRD negative status at a sensitivity of 10^{-6} in patients achieving CR.
- Duration of MRD negativity (10^{-6}) in patients who achieve MRD negative status at CR.
- Evaluation of generic HRQOL/health status, measured by the EQ-5D-5L instrument.

5.3.4 Estimands

Estimand: ORR in Part 3	Primary Estimand
Definition	The treatment effect of modakafusp alfa in the full analysis set
Treatment	Modakafusp alfa 120mg and 240mg
Population	Full analysis set: including all patients who receive at least 1 dose of the study drug even an incomplete dose, of modakafusp alfa, in the Part 3 extension cohorts.
Variable (or Endpoint)	ORR, defined as the proportion of patients who achieved a confirmed sCR, CR, VGPR, or PR during the study as defined by IMWG Uniform Response Criteria
Strategy for Addressing Intercurrent Event	Hypothetical strategy for subsequent anti-cancer therapy (intercurrent event): The disease assessments after subsequent therapy will be censored. Treatment policy strategy for treatment discontinuation (intercurrent event): The disease assessment after treatment discontinuation will be included for evaluation
Population-Level Summary	Observed ORR with 95% CI

6.0 DETERMINATION OF SAMPLE SIZE

Part 1 of the study will follow a standard 3+3 dose escalation design. Under this design, the probability of dose escalation according to the true DLT rate is as follows:

True DLT rate	5%	10%	20%	30%	40%	50%	60%	70%
Probability of escalating	97%	91%	71%	49%	31%	17%	8%	3%

DLT: dose-limiting toxicity.

The above probability is calculated by summing up the probability of the two below events that leads to dose-escalation:

- a) no DLT in the first cohort of 3 patients at a dose level, or
- b) One DLT in the first cohort of 3 patients and no DLT in the second cohort of 3 patients at a dose level.

The probability of not observing a DLT in a sample size of 6 patients according to the true DLT rate is as follows:

True DLT rate	5%	10%	20%	30%	40%	50%	60%	70%
Probability of no toxicity	74%	53%	26%	12%	4.7%	1.6%	0.4%	<0.1%

DLT: dose-limiting toxicity.

Patients will be considered evaluable in phase 1 for MTD/OBD assessment provided that they have not missed any of their infusions of modakafusp alfa in Cycle 1 or have had a DLT. Patients who are not considered evaluable as defined above will be replaced.

Part 2 Expansion

The number of patients in the dose expansion phase was determined based on a binomial exact test design. A sample size of 25 patients will allow a cohort to have over 80% power to rule out an uninteresting response rate of 10% if the true response rate is 30% with a one-sided alpha of 0.05. A Bayesian predictive probability design is used to allow multiple interim analyses to stop early for futility. The study will enroll up to 25 patients in each cohort to further characterize safety of the OBD/MTD and obtain preliminary clinical efficacy data. With a vague beta prior with shape parameters 0.428 and 1 for ORR (i.e., mean of 30%), 11 responders out of 25 gives a greater than 90% posterior probability of true ORR being greater than 30%. An OBD/MTD dose will be considered clinically relevant if 11 out of 25 response evaluable patients have a confirmed PR or better. The design has reasonable operating characteristics. With a true ORR of 30%, the probability of declaring success is 7%. In contrast, with a true ORR of 50%, the probability of declaring success is 70%.

See Section 7.13 for details of futility analyses after 10 and 15 evaluable patients are enrolled in the expansion phase.

Part 3 Extension

The primary objective of Part 3 of the study is to determine the confirmed ORR, including PR, VGPR, CR, and sCR assessed according to the IMWG criteria to modakafusp alfa in patients with MM previously treated with ≥ 3 lines and with evidence of disease progression who are refractory to, or intolerant of, a PI, an IMiD, and an anti-CD38 mAb (triple refractory). The sample size was determined to claim that the true ORR is greater than the threshold response rate of 20% within each treatment arm. A total sample size of approximately 236 enrolled patients (118 patients per arm) will allow the study to have over 90% power to rule out an uninteresting response rate of 20% if the true rate is 35% with a 1-sided alpha of 0.025.

The purpose of the China continuation cohort is to allow continued evaluation of efficacy and any emerging safety signals in Chinese patients enrolled in China. After global patient enrollment is completed in Part 3, enrollment will continue for the China continuation cohort until about 15% of the total sample size is reached at the selected dose(s) (eg, 18 patients based on 118 patients treated at the selected dose[s]).

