13.3 Determination of Sample Size

Part 1 of the study will follow a standard 3 + 3 dose escalation design. Under this design, the probability of dose escalation according to the true DLT rate is as follows:

True DLT rate	5%	10%	20%	30%	40%	50%	60%	70%
Probability of escalating	97%	91%	71%	49%	31%	17%	8%	3%

DLT: dose-limiting toxicity.

The probability of not observing a DLT in a sample size of 6 patients according to the true DLT rate is as follows:

True DLT rate	5%	10%	20%	30%	40%	50%	60%	70%
Probability of no toxicity	74%	53%	26%	12%	4.7%	1.6%	0.4%	<0.1%

DLT: dose-limiting toxicity.

Patients will be considered evaluable in Part 1 for MTD/OBD assessment provided they have not missed any of their infusions of modakafusp alfa in Cycle 1 and have not had a DLT. Patients who are not considered evaluable as defined above will be replaced.

Part 2 Expansion

The study will enroll up to 25 patients in each arm to further characterize safety of the OBD/MTD and obtain preliminary clinical efficacy data. An OBD/MTD dose will be considered clinically relevant if at least 11 out of 25 response evaluable patients have a confirmed PR or better. With a vague beta prior with shape parameters 0.428 and 1 for ORR (ie, mean of 30%), 11 responders out of 25 gives a greater than 90% posterior probability of true ORR being greater than 30%. The design has reasonable operating characteristics. With a true ORR of 30%, the probability of declaring success is 7%. In contrast, with a true ORR of 50%, the probability of declaring success is 70%.

Part 3 Extension

The primary objective of Part 3 of the study is to determine the confirmed ORR, including PR, VGPR, CR, and sCR assessed according to the IMWG criteria (Appendix F) to modakafusp alfa in patients with MM previously treated with ≥3 lines and with evidence of disease progression who are refractory to, or intolerant of, a PI, an IMiD, and an anti-CD38 mAb (triple refractory). The sample size was determined to claim that the true ORR is greater than the threshold response rate of 20% within each treatment arm. A total sample size of approximately 236 enrolled patients (118 patients per arm) will allow the study to have over 90% power to rule out an uninteresting response rate of 20% if the true rate is 35% with a 1-sided alpha of 0.025.

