7.8 Efficacy Analysis

7.8.1 Part 1 and Part 2 Efficacy Analysis

Response evaluations after the start of subsequent anti-cancer therapy will not be considered in the calculation of efficacy endpoints, while the response evaluation after the treatment discontinuation will be considered in the calculation of efficacy endpoints. Please refer to Section 7.9.2 Part 3 Efficacy Analysis for details. When appropriate, data from patients in the

expansion cohorts will be summarized together with data from patients in the dose escalation phase.

Objective Response Rate (ORR)

The ORR is defined as the proportion of patients who achieved a confirmed PR or better during the study per investigator assessment as defined by IMWG Uniform Response Criteria. The ORR will be summarized by frequencies, percentages, and the exact two-sided 95% CIs based on the safety analysis set.

Clinical Benefit Rate (CBR)

The CBR includes patients with a confirmed response of sCR, CR, VGPR, PR, or MR during the study per investigator assessment as defined by IMWG Uniform Response Criteria. The CBR will be summarized by frequencies, percentages, and the exact two-sided 95% CIs based on the safety analysis set.

Disease Control Rate (DCR)

The DCR includes patients with a confirmed response sCR, CR, VGPR, PR, MR, or SD during the study per investigator assessment as defined by IMWG Uniform Response Criteria. The DCR will be summarized by frequencies, percentages, and the exact two-sided 95% CIs based on the safety analysis set.

Duration of Response (DOR)

The DOR will be calculated for those patients with a confirmed PR or better in the safety analysis set. The DOR is defined as the time from the first documentation of a confirmed response until progressive disease or death, whichever comes first. If there is no progressive disease or death observed, it will be censored at the last adequate response assessment. Please refer to Table 1 for the detailed censoring rules.

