7.13 Interim Analyses and Criteria for Early Termination

Part 2

A futility analysis will be conducted when 10 response-evaluable patients in a phase 2 arm have been followed for at least 3 cycles or have already responded or withdrawn. An arm with the predictive probability <15% (i.e., 3 or fewer responders in 10 patients) will stop enrollment for futility. Overall, avoidance of futility requires 11 or more responders out of the 25 patients to achieve 90% of the overall posterior probability of success (PPOS) at the final analysis. Unless all 25 patients have already been enrolled, another futility analysis with the same decision rule based on PPOS will be conducted when 15 response-evaluable patients in a phase 2 arm have been followed for at least 3 cycles or have already responded or withdrawn. If there are 5 or fewer responders in 15 patients, enrollment will stop for futility. However, the study team reserves the rights to continue the study if the patients still benefit from the study drug.

Part 3

In the Part 3 extension cohorts, an independent data monitoring committee (DMC) will review accumulating safety, tolerability, and efficacy data. The first DMC meeting will occur after approximately 20 patients (approximately 10 patients from each arm) have been enrolled and treated. The second and third DMC meeting will occur at the first and second interim futility analysis when approximately 30 and 96 patients (approximately 15 and 48 patients from each arm) have been enrolled and have completed 3 cycles of treatment or discontinue the treatment prematurely. The subsequent DMC meetings will be approximately every 6 months thereafter.

Futility Stopping Rules

Two interim analyses for futility are planned for the Part 3 extension cohorts when approximately 15 and 48 patients of the planned 118 patients per arm are enrolled and treated for at least 3 cycles or have discontinued treatment prematurely. The futility stopping boundary will be determined based on the predictive probability of success at the primary analysis, using a Bayesian efficacy monitoring approach. The treatment arm will be dropped for futility if the predictive probability of success at the primary analysis is found to be <10% based on the data

CONFIDENTIAL

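### SAP 6.0 supports the 25-patient Part 2 cohorts with over 80% power at a true ORR of 30%, but under the plan's only success rule (at least 11 of 25) the chance of success at that rate is 7.6% to 9.8%

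*SAP*

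**What the plan says.** SAP 6.0 (Part 2 Expansion) opens with the basis for the cohort size: "The number of patients in the dose expansion phase was determined based on a binomial exact test design". It continues: "A sample size of 25 patients will allow a cohort to have over 80% power to rule out an uninteresting response rate of 10" per cent, "if the true response rate is 30% with a one-sided alpha of 0.05".

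The same paragraph then sets a different criterion. With a Beta(0.428, 1) prior, 11 responders of 25 give more than 90% posterior probability that the ORR exceeds 30%, and a dose is called clinically relevant on that result. The operating characteristics follow: "With a true ORR of 30%, the probability of declaring success is 7" per cent, and 70% at a true ORR of 50%.

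SAP 7.13 repeats the threshold: "Overall, avoidance of futility requires 11 or more responders out of the 25 patients". It stops a cohort for futility at 3 or fewer responders of 10, or 5 or fewer of 15, but adds: "However, the study team reserves the rights to continue the study if the patients still benefit from the study drug".

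For the analysis of Part 2 ORR, SAP 7.8.1 says: "The ORR will be summarized by frequencies, percentages, and the exact two-sided 95% CIs based on the safety analysis set".

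Protocol 13.3 has the same rule, "clinically relevant if at least 11 out of 25 response evaluable patients have a confirmed PR or better", with the same 7% and 70%. It has no statement of power against 10%.

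**The concern.** For one sample size, one endpoint and one true rate (30%), SAP 6.0 gives two very different chances of a favourable outcome, over 80% and 7%, and does not say that they belong to different rules. In the power sentences 30% is the rate the cohort should detect. In the decision rule 30% is the rate to be exceeded.

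ORR is the Part 2 primary endpoint. A reader who takes the power sentence as the justification for 25 patients would expect a cohort with a true ORR of 30% to succeed, when the rule is built so that such a cohort usually fails.

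**Working it through.** **Inputs.** n = 25; null 10%, alternative 30%, one-sided alpha 0.05 (SAP 6.0). Success at 11 or more (Protocol 13.3, SAP 6.0 and 7.13). Prior Beta(0.428, 1) (SAP 6.0). Futility stops at ≤3/10 and ≤5/15 (Protocol 13.2.1, SAP 7.13).

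**1. Reproducing the 80%.** P(X ≥ r | p) = Σ C(25, x) pˣ (1 − p)²⁵⁻ˣ, summed over x from r to 25.

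| Success cut-off | P at ORR 10% (alpha) | P at ORR 30% |
|---|---|---|
| ≥5 | 0.0980 | 0.9095 |
| ≥6 | 0.0334 | 0.8065 |
| ≥7 | 0.0095 | 0.6593 |
| ≥11 | 0.00001 | 0.0978 |

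The smallest cut-off that keeps alpha at or below 0.05 is 6, with power 80.65%. The SAP figure is therefore right for a 6-of-25 test with no interim stopping.

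**2. Which rule the plan uses.** The posterior after x responders is Beta(0.428 + x, 26 − x). P(ORR > 30%) is 0.841 at x = 10 and 0.920 at x = 11, so 11 is the correct cut-off for the 90% criterion. The predictive probability of reaching 11 is 0.134 after 3/10 and 0.124 after 5/15. Both are below the 15% limit, while 4/10 gives 0.390 and 6/15 gives 0.370. The futility stops are thus calibrated to 11 of 25.

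**3. Chance of success under that rule.** At ORR 30%:

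- P(stop at 10) = P(X₁₀ ≤ 3) = 0.6496.
- P(pass at 10, stop at 15) = 0.1230.
- P(pass both) = 1 − 0.6496 − 0.1230 = 0.2274.
- P(success) = Σ P(X₁₀ ≥ 4, X₁₅ = s) × P(Bin(10, 0.3) ≥ 11 − s), over s ≥ 6, = 0.0758.

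The same calculation for the other cases:

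| Futility stops followed | ORR 30% | ORR 50% |
|---|---|---|
| Both | 7.6% | 69.8% |
| Look at 10 only | 8.0% | 71.4% |
| Neither | 9.8% | 78.8% |

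The printed 7% and 70% match the first row to within one point.

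**4. Size of the gap.** With no stopping, 80.65% − 9.78% = 70.87%. This is P(6 ≤ X ≤ 10 | 30%), the share of full cohorts that would pass a 6-of-25 test and fail the plan's rule.

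**5. Whether the planned interval supplies the power.** The lower limit of the exact two-sided 95% CI is 9.4% at 6/25 and 12.1% at 7/25. Excluding 10% therefore needs at least 7 responders, with probability 65.9% at ORR 30% before any futility stopping.

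**The case against.** The best defence is that the two figures answer different questions. One is the power to exclude 10%; the other is the chance that a dose is called clinically relevant. Both can be true of 25 patients, and the SAP never says that the 80% is the chance of reaching 11. The 7% is printed a few sentences later, so the low success probability is disclosed. The protocol is silent on 10% versus 30% and does not contradict it. The threshold, the futility cut-offs and the 7% and 70% agree across both documents. Part 2 is a preliminary evaluation, and nothing here reaches the Part 3 sample size or success rule.

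Much of this stands, and it limits the harm. SAP 6.0 does name a 10% null; what is missing is any decision rule or analysis step that uses it. It would also prove little to apply the futility stops to the 6-of-25 test. That gives 22.7%, but this is simply the chance of passing both looks, because passing the second already requires 6 responders.

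The defence does not rescue the sentence. SAP 6.0 presents the 10% versus 30% test as the way the sample size was set. No planned analysis delivers its power, and the text does not separate it from the rule that decides.

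**Conclusion.** The concern holds. The over-80% figure is arithmetically correct but describes a test that the plan does not run. Under the operative rule, the chance of success at a true ORR of 30% is 7.6% with both futility stops followed and 9.8% with neither, against the 80.7% that the power sentence implies.

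These figures assume independent responses with a common rate and exactly 25 response-evaluable patients, with looks at exactly 10 and 15. The range covers the override allowed in SAP 7.13 and the omission of the second look when all 25 are already enrolled.

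This is an inconsistency of justification within the SAP, in text that the protocol does not carry. The Part 2 decision is not in doubt: 6 to 10 responders fail the only stated criterion.

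**What to change.** In SAP 6.0, delete the sentence on the exact binomial design and the one on power against 10%. Alternatively, keep them labelled as a separate reference calculation (10% versus 30%, at least 6 of 25, no futility stopping) that is not the success criterion.

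Keep 11 of 25 as the sole criterion, worded as a minimum, as Protocol 13.3 and SAP 7.13 already have it. State its operating characteristics with the futility assumption: about 8% at ORR 30% and 70% at ORR 50% if both stops are followed, rising to about 10% and 79% if they are overridden.

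The cost is SAP wording only. Conduct, data and the decision rule are unchanged; what is lost is the 80% headline.

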7.0 METHODS OF ANALYSIS AND PRESENTATION

For Part 3, two interim analyses for futility are planned when approximately 15 and 48 patients of the planned 118 patients per arm are enrolled and treated for at least 3 cycles or discontinued treatment prematurely. Details of the interim analyses can be referred to Section 7.13.

The planned primary analysis will be performed once the study reaches 6 months after the last patient is randomized and treated. An updated analysis for PFS, DOR, and OS will be performed at the end of study.

7.1 General Principles

All statistical analyses will be conducted using SAS[®] Version 9.4 or later.

For categorical variables, the count and proportions of each possible category value will be tabulated. The denominator for the proportion will be based on the number of subjects in the analysis sets. For continuous variables, the mean, median, standard deviation, minimum, and maximum values will be presented for all patients in the relevant analysis set.

Means and medians will be presented to 1 more decimal place than the recorded data. The standard deviations will be presented to 2 more decimal places than the recorded data.

Confidence intervals about a parameter estimate will be presented using the same number of decimal places as the parameter estimate.

All confidence intervals, statistical tests, and resulting P-values will be reported as 2-sided. P-values should be presented to 3 decimal places, with values less than 0.001 presented as <0.001.

Baseline values are defined as the last observed value before the first dose of study drug.

7.1.1 Data Presentations

Part 1 and Part 2

1. Baseline evaluations/disposition/medical history/concurrent medical condition/concomitant medication/medication history/prior therapy:

Data will be presented by schedule within dose escalation, dose expansion, and in overall study population.

Dose escalation

Schedule A	Schedule B	Schedule C	Schedule D	Total
------------	------------	------------	------------	-------

Dose expansion

Schedule A MTD/OBD	Schedule B MTD/OBD	Schedule C MTD/OBD	Schedule D MTD/OBD	Schedule X + Dex MTD/OBD	Total
-----------------------	-----------------------	-----------------------	-----------------------	-----------------------------	-------

Study overall

Dose Escalation Total	Dose Expansion Total	Total
-----------------------	----------------------	-------

2. Safety/Efficacy/Pharmacokinetic/Pharmacodynamic

Data will be presented by dose level within dose escalation and dose expansion, and in overall study population.

Dose escalation: by dose level within each schedule

Schedule A (repeat for schedule B, C, and D):

Dose Level 1	Dose Level 2	Dose Level 3	Continue for each dose level	Total
--------------	--------------	--------------	---------------------------------	-------

Dose expansion:

Present for each schedule MTD/OBD dose level explored in the expansion.

Schedule: TBD Dose Level mg/kg (+ Dexamethasone)

Schedule A MTD/OBD	Schedule B MTD/OBD	Schedule C MTD/OBD	Schedule D MTD/OBD	Schedule X MTD/OBD + Dex
-----------------------	-----------------------	-----------------------	-----------------------	--------------------------------

Study overall

Dose Escalation Total	Dose Expansion Total	Total
-----------------------	----------------------	-------

Part 3

1. Baseline evaluations/disposition/medical history/concurrent medical condition/concomitant medication/medication history/prior therapy/safety:

Data will be presented by dose level and the overall study population.

120mg	240mg	Total
-------	-------	-------

2. Efficacy/Pharmacokinetic/Pharmacodynamic

Data will be presented by dose level.

120mg	240mg
-------	-------

7.1.2 Definition of Study Days

Study Day 1 is defined as the date on which a subject is administered with their first dose of the study drug. Other study days are defined relative to the Study Day 1 with Day 1 being Study Day 1 and Day -1 being the day prior to Study Day 1.

7.1.3 Methods for Handling Missing Data

For efficacy and safety data, no imputation of values for missing data will be performed.

Imputation rules for incomplete dates are described in Appendix B.

7.1.4 Extended Loss-to-Follow-up

For subjects, if two or more scheduled disease assessments are missed and are then followed by an assessment of PD or death, PFS, DOR, and TTP will be censored at the last adequate assessment prior to PD or death. If the scheduled disease assessment is every 4 weeks (Schedule A, B, and D), a window of 64 days will be used to determine whether there was an extended time without adequate assessment. That is, if the time difference between PD/death and last adequate assessment is more than 64 days, then PFS, DOR and TTP will be censored at the last adequate assessment prior to PD/death. If the scheduled disease assessment is every 3 weeks (Schedule C), a window of 50 days will be used to determine whether there was an extended time without adequate assessment.

